2.2 Analysis of the secondary efficacy endpoints

Summary statistics (n, mean, standard deviation, median, the first quartile (Q1), the third quartile (Q3), minimum, and maximum) will be provided by age cohort within each dose group as well as in the overall group for the measurement at each visit and change from baseline values for the following secondary efficacy variables:

- Central venous pressure (CVP)
- Left atrial pressure (LAP)
- Pulmonary artery pressure (PAP- systolic and diastolic)
- Central venous and arterial oxygen saturation
- Urine output
- Blood lactate levels (arterial and central venous lactate)

The safety set will be used for the above analyses. Data collected at the following assessment time points/visits will be included in the analyses: at baseline, prior to each dose escalation, at 48 hours post infusion start, and at 24 hours post end of infusion.

Clinical Development

RLX030/Serelaxin

Study No. CRLX030A2208 / NCT02151383

Multicenter, open-label, dose escalation study to evaluate safety, tolerability and pharmacokinetics of RLX030 in addition to standard of care in pediatric patients from birth to <18 years of age, hospitalized with acute heart failure

Module 3 – Detailed Statistical Methodology

Amendment 1

Author(s):  Trial Statistician

Document type: RAP Documentation Amendment

Document status: Final

Release date: 29-Jun-2017

[figure not shown]
Number of pages:

Property of Novartis
Confidential
May not be used, divulged, published or otherwise disclosed
without the consent of Novartis

Table of contents

Table of contents	3
List of tables	4
List of abbreviations	5
	
1 Introduction	6
2 Analysis sets	7
3 Subgroup definitions	9
4 Baseline and post baseline definitions	9
5 Subject Disposition, background and demographic characteristics	10
5.1 Subject disposition	10
5.2 Protocol deviations	10
5.3 Background and demographic characteristics	10
5.4 Medical History	11
6 Study medication	11
7 Concomitant medication	11
8 Pharmacokinetic (PK) data	11
9 Selected vital signs for safety (SBP, DBP, HR and RR)	11
10 Adverse Events (AEs), SAEs and Deaths	11
11 Other data	12
12 Interim analyses	13
13 Sample size and power considerations	13
14 Appendix 1 - Reference	13

List of tables

Table 2-1	Rules for subject classification in the analysis sets based on protocol deviations and non-protocol deviation classification criteria	8
Table 3-1	Specification of subgroups.....	9

List of abbreviations

AE	Adverse Event
BP	Blood Pressure
[REDACTED]	[REDACTED]
SBPDE	Systolic Blood Pressure Decrease Event
CSR	Clinical Study Report
[REDACTED]	[REDACTED]
DBP	Diastolic Blood Pressure
ECG	Electrocardiogram
ES	Enrolled Set
FAS	Full Analysis Set
HR	Heart Rate
[REDACTED]	[REDACTED]
MedDRA	Medical Dictionary for Regulatory Affairs
[REDACTED]	[REDACTED]
PK	Pharmacokinetics
PT	Preferred Term
PSRC	Pediatric Safety Review Committee
Q1	the First Quartile
Q3	the Third Quartile
RR	Respiratory Rate
SAE	Serious Adverse Event

SAF	Safety Set
SBP	Systolic Blood Pressure
SCR	Screened Set
SOC	System Organ Class
[REDACTED]	[REDACTED]
[REDACTED]	[REDACTED]

1 Introduction

This document provides details of the statistical analyses to support the completion of the abbreviated Clinical Study Report (CSR) for the study CRLX030A2208. Due to the early termination of the study, the planned analyses for a full/complete CSR (as outlined in the study protocol) may not provide clinically and/or statistically meaningful results. Therefore, an abbreviated CSR is planned for the study CRLX030A2208. No efficacy analysis will be performed for the abbreviated CSR: PK parameters and other derived efficacy parameters (as defined in the study protocol) will not be provided; Non-derived efficacy parameters (as outlined in the study protocol), if available, will be listed at the individual patient level. Other data will be listed with the following exceptions:

Summary tables will be provided for the following non-efficacy data:

- Disposition (see [Section 5.1](#))
- Demographic and background characteristics (see [Section 5.3](#))
- Safety data
 - Treatment emergent non-serious AEs (see [Section 10](#))
 - Treatment emergent SAEs (see [Section 10](#))
 - Treatment emergent AEs (including non-serious AEs and SAEs) (see [Section 10](#))
 - Treatment emergent AEs leading to discontinuation (see [Section 10](#))
 - Deaths (see [Section 10](#))
 - Vital signs (selected) (see [Section 9](#))
 - Systolic blood pressure (SBP)
 - Diastolic blood pressure (DBP)
 - Heart rate (HR)
 - Respiratory rate (RR)

In general, continuous variables will be summarized descriptively by n, mean, SD, median, minimum (min), Q1 (25th percentile), Q3 (75th percentile) and maximum (max), while categorical variables will be summarized by count and percentage of patients in each category. Unless otherwise specified, data will be summarized or listed by **dose group** (RLX low dose group: 3 µg/kg/day, 10 µg/kg/day and 30 µg/kg/day; RLX high dose group: 10 µg/kg/day, 30 µg/kg/day and 100 µg/kg/day) and **age cohort** (Age cohort 1: 6 to < 18 years; Age cohort 2: 1 to <6 years; Age cohort 3: infants 1 month to <1 year; Age cohort 4: neonates birth to <1 month).

Other data, including safety parameters, PK concentrations etc. will be listed at the individual patient level. In addition, graphical presentation of PK concentration vs. time will be provided.

2 Analysis sets

The following analysis populations will be defined for the statistical analysis:

- **Screened set (SCR)** – All subjects for whom valid informed consent from a parent or legal guardian was obtained.
- **Enrolled set (ES)** – All subjects in the SCR to whom study treatment has been assigned, regardless of trial medication received.
- **Safety set (SAF)** – All subjects in the ES who were exposed to study drug regardless of the exposure and have at least one post-baseline safety assessment. Of note, the statement

that a subject had no adverse event (AE) also constitutes a safety assessment. Subjects will be analyzed according to treatment received.

- **The PK analysis set (PK)** will include all subjects with at least one available valid (i.e. not noted for exclusion) PK concentration measurement, who received study drug and experienced no protocol deviations with relevant impact on PK data. Subjects will be analyzed according to treatment received.

The number and percentage of patients in each analysis set will be summarized by age cohort within each treatment group if applicable and for all patients. Patients excluded from any analysis set will be listed for the safety population.

Table 2-1 Rules for subject classification in the analysis sets based on protocol deviations and non-protocol deviation classification criteria

Analysis set	Protocol Deviations (PDs) leading to the exclusion of a subject		Non-PD criteria leading to the exclusion of a subject
	Protocol Deviation ID	Description of the PD	
Screened set	INCL01	Written informed consent by parent/legal guardian was NOT obtained before any study-specific assessment, that is done specifically for the study, was performed.	
Enrolled set	INCL01	Written informed consent by parent/legal guardian was NOT obtained before any study-specific assessment, that is done specifically for the study, was performed.	
Safety set	INCL01	Written informed consent by parent/legal guardian was NOT obtained before any study-specific assessment, that is done specifically for the study, was performed.	No study medication given during the treatment period
PK analysis set	INCL01	Written informed consent by parent/legal guardian was NOT obtained before any study-specific assessment, that is done specifically for the study, was performed.	No study medication given during the treatment period; No valid PK concentration measurement

3 Subgroup definitions

In Table 3-1, we have listed all subgroups defined for this study. In general, subgroups will be defined based on baseline information. Age cohort will be used throughout the analyses. Count and percentage of etiology subgroups will be provided as part of the patient demographic and background information.

Table 3-1 Specification of subgroups

Subgroup	Method of Derivation	Disposition /Background & demo. /Exposures	PK analysis	Safety
Age cohort (at screening [REDACTED]): Age cohort 1: 6 to <18 years; Age cohort 2: 1 to <6 years; Age cohort 3: 1 month* to <1 year; Age cohort 4: birth to <1 month*	eCRF	x	x	x
Etiology subgroups [REDACTED]: Post-surgical etiology Medical etiology	eCRF	x		

*1 month = 30 days.

4 Baseline and post baseline definitions

Baseline definition

For the selected vital signs (SBP, DBP, HR and RR), baseline is defined as the measurement obtained on Day 1 [REDACTED], or the sample obtained at an earlier visit (scheduled or

unscheduled) which was closest to Day 1 [REDACTED], if the Day 1 [REDACTED] measurement is missing.

5 Subject Disposition, background and demographic characteristics

5.1 Subject disposition

The number and percentage of patients in each analysis set, safety patients who discontinued from the study and the reasons for discontinuation will be summarized by age cohort within each treatment group and in the overall group. The screened set (SCR) will be used.

In addition, the reasons for screen failures, based on inclusion/exclusion criteria, will be listed at the individual patient level for the SCR.

5.2 Protocol deviations

Protocol deviations will be pre-specified and finalized for analyses prior to database lock. All protocol deviations will be listed at the individual patient level for the SAF.

5.3 Background and demographic characteristics

The following demographic and background characteristics data [REDACTED]

[REDACTED] will be summarized descriptively (using n, mean, standard deviation, median, Q1, Q3, minimum, and maximum for continuous variables; or number and percentage for categorical variables) for the SAF by age cohort within each treatment, and in the overall group (Note: Categorical variables are underlined. Variables without an underline are continuous variables):

- Age (years)
- Sex: Male; Female
- Race: Caucasian; Black; Asian; Native American; Pacific Islander; Unknown; Other
- Ethnicity: Hispanic or Latino; East Asian; Southeast Asian; South Asian; West Asian; Russian; Mixed Ethnicity; Not Reported; Unknown; Other
- Weight (kg)
- Height (cm)
- Etiology: Post-surgical; Medical
- Genetic/chromosomal abnormalities: Yes; No; Unknown
- Clinical syndrome without genetic diagnosis: Yes; No; Unknown
- Malformation of an organ system other than the heart: Yes; No; Unknown

All demographic and background characteristic data, including delivery history (only for age cohort 3 or 4 patients) will be listed at the individual patient level for the SAF.

5.4 Medical History

Medical history entered on the medical history CRF page at screening [REDACTED] will be coded using the MedDRA dictionary. Medical history and protocol solicited events (only for post-surgical patients) will be listed at the individual patient level for the SAF.

6 Study medication

Data entered on the Dosage Administration Record CRF page will be listed at the individual patient level for the SAF. This will include dose prescribed (ug/kg/day), start/end date and time of the infusion, concentration (ug/ml), rate of infusion (mL/h) and reason for the dosage administered.

7 Concomitant medication

Prior and concomitant medications, continuous intravenous concomitant medications, surgical and medical procedures and use of mechanical ventilator will be listed at the individual patient level for the SAF. The medication name will be coded using therapeutic class (ATC code) and preferred term (PT).

8 Pharmacokinetic (PK) data

PK concentration data will be listed at the individual patient level for the SAF. Invalid PK concentration data will be noted. A graphical presentation will be employed to show individual serelaxin concentration-time (actual) profiles by age cohort within each dose group. These figures will be prepared for the PK analysis set.

9 Selected vital signs for safety (SBP, DBP, HR and RR)

Summary statistics (n, mean, standard deviation, median, Q1, Q3, minimum, and maximum) will be provided by age cohort within each dose group for the measurement at each visit and change from baseline values for the following parameters for the safety population:

- Systolic blood pressure (SBP)
- Diastolic blood pressure (DBP)
- Heart rate (HR)
- Respiratory rate (RR)

10 Adverse Events (AEs), SAEs and Deaths

A treatment emergent adverse event is defined as an adverse event that occurs at or after the start of the study treatment. Treatment emergent adverse events including non-serious AEs, SAEs, AEs (including non-serious AEs and SAEs) and AEs leading to discontinuation will be

summarized descriptively (using number and percentage) by age cohort within each treatment group and in the overall group. Similarly, deaths will be summarized descriptively as appropriate. The number and percentage of these events will be presented by system organ class (SOC) and MedDRA preferred term (PT). All AEs will be listed at the individual patient level. These analyses will be performed for the SAF.

In addition, SAEs in screen failure patients will be listed at the individual patient level.

11 Other data

Other data will be listed at the individual patient level as appropriate. The following data will be listed for the SAF, and listings marked with “*” will be subject to data availability:

- Local lab (including chemistry, hematology and urinalysis)
- Central lab (including chemistry and hematology)
- Vital signs and clinical assessment
- Ventilation/respiratory parameters (if on mechanical ventilation)
- * Systolic Blood Pressure Decrease Event (SBPDE)
- * Vital signs – SBPDE monitoring
- * Ventilation/respiratory parameters – SBPDE monitoring
- * Vital signs – AE suggestive of Worsening Heart Failure (WHF) monitoring
- * Ventilation/respiratory parameters – AE suggestive of Worsening Heart Failure (WHF) monitoring
- Echocardiography
- [REDACTED]
- ECG
- [REDACTED]
- [REDACTED]

[REDACTED] eGFR (as part of the central laboratory data) will be calculated using the Schwartz formula (Schwartz et al. 2009): eGFR (mL/min/1.73m²) = 0.41 x height (cm)/serum creatinine (mg/dL).

Mean arterial pressure, derived as [(2 x DBP) + SBP] ÷ 3 (Cywinski 1980), will be included in listings of the vital signs data. Notably abnormal vital signs (SBP, DBP, HR and RR) [REDACTED] will be noted in data listings.

12 Interim analyses

There will be no formal interim analysis for this study. However, there will be interim PK and safety data reviews by the Pediatric Safety Review Committee (PSRC). See Section 3.1 of the study protocol for study design details.

[REDACTED]

13 Sample size and power considerations

Sample size is guided by feasibility in pediatric patient studies for assessment of safety, tolerability and pharmacokinetics.

The sample size planned for the high-dose group (10/30/100 µg/kg/day) per age cohort will be 6 subjects or 3 subjects (see Section 3.1 of the study protocol v04 for the study design details). With a sample size of 6 subjects per age cohort, receiving RLX030 at various doses, there is ~80% probability to observe an adverse event with an underlying occurrence rate of 24% at least once for each cohort and dose combination during the study. With a sample size of 3 subjects per age cohort, receiving RLX030 at various doses, there is ~56% probability to observe an adverse event with an underlying occurrence rate of 24% at least once for each cohort and dose combination during the study.

Data from 6 subjects will also provide ~80% probability for the 95% confidence intervals (CI) of geometric means of RLX030 Css to fall within the range of (68%U, 146%U), data from 3 subjects will provide ~80% probability for the 95% confidence intervals (CI) of geometric means of RLX030 Css to fall within the range of (39%U, 257%U), where U is the observed geometric mean, assuming a coefficient of variation of 30% [REDACTED].

[REDACTED] An additional 3 subjects in each age cohort, will be enrolled into a low-dose group (3/10/30 µg/kg/day). The purpose of this low-dose group is to further enhance the safety by collecting safety data at a starting dose of 3 µg/kg/day up to the adult efficacious dose of 30 µg/kg/day, before enrolling patients in the high-dose group.

These calculations were performed using nQuery.

14 Appendix 1 - Reference

Schwartz GJ, Work DF (2009) Measurement and Estimation of GFR in Children and Adolescents. Clin J Am Soc Nephrol 4: 1832–1843

Cywinski J (1980) The essentials in pressure monitoring (Martinus Nijhoff Publishers b.v. Boston): 23–24.

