5.1 Protocol requested treatment

5.1.1 Investigational treatment

Escalating doses of serelaxin will be administered in a continuous iv infusion for a total of 48 hours. Dose rates of 3 $\mu\text{g}/\text{kg}/\text{day}$, 10 $\mu\text{g}/\text{kg}/\text{day}$ and 30 $\mu\text{g}/\text{kg}/\text{day}$ will be used in the low-dose group and dose rates of 10 $\mu\text{g}/\text{kg}/\text{day}$, 30 $\mu\text{g}/\text{kg}/\text{day}$ and 100 $\mu\text{g}/\text{kg}/\text{day}$ will be used in the high-dose group.

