5.5.13 Study completion and post-study treatment

Patient participation will be completed 28 days after the start of the study drug infusion. The investigator must provide follow-up medical care for all patients who are prematurely withdrawn from the study, or must refer them for appropriate ongoing care.

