6.5 Safety

6.5.1 Physical examination

A complete physical examination will be performed by the investigational staff at screening and include the examination of general appearance, skin, neck (including thyroid), eyes, ears, nose, throat, lungs, heart, abdomen, back, lymph nodes, extremities, vascular and neurological. An abbreviated physical examination will be performed at all other visits and before every dose escalation as part of the global hemodynamic assessment noted in [Section 5.5.4](#), and is to include the examination of general appearance and vital signs.

Information for all physical examinations must be included in the source documentation at the study site. Significant findings that are present prior to signing informed consent must be included in the Medical History part of the eCRF. Significant findings related to the physical examination made after signing the informed consent, up to and including Day 14, which meet the definition of an AE must be recorded on the Adverse Event section of the eCRF ([Section 7.1](#)). Significant findings related to the physical examination made after signing the informed consent, up to and including Day 14, which meet the definition of a SAE must be recorded on the Serious Adverse Event section of the eCRF ([Section 7.2](#)), and a completed signed Serious Adverse Event form must be provided to the local Novartis Drug Safety and Epidemiology Department (DS&E) faxed within 24 hours after awareness of the SAE.

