7.2.2 Serious adverse event (SAE) reporting

To ensure subject safety, every SAE, regardless of causality, occurring after the subject has provided informed consent and until 30 days after the last study visit must be reported to Novartis within 24 hours of learning of its occurrence. Any SAEs experienced after the 30 days period should only be reported to Novartis if the Investigator suspects a causal relationship to study treatment.

Recurrent episodes, complications, or progression of the initial SAE must be reported as follow-up to the original episode, regardless of when the event occurs. This report must be

[REDACTED]

[REDACTED]

submitted within 24 hours of the Investigator receiving the follow-up information. An SAE that is considered completely unrelated to a previously reported one should be reported separately as a new event.

Information about all SAEs is collected and recorded on the Serious Adverse Event Report Form; all applicable sections of the form must be completed in order to provide a clinically thorough report. The investigator must assess the relationship of each SAE to the study drug, complete the SAE Report Form in English, and submit the completed form within 24 hours to Novartis. Detailed instructions regarding the submission process and requirements for signature are to be found in the investigator folder provided to each site.

Follow-up information is submitted as instructed in the investigator folder. Each re-occurrence, complication, or progression of the original event must be reported as a follow-up to that event regardless of when it occurs. The follow-up information should describe whether the event has resolved or continues, if and how it was treated, whether the blind was broken or not, and whether the patient continued or withdrew from study participation.

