9.5.2 Safety variables

Adverse events, SAEs and Death

Adverse events (AEs, SAEs and AEs leading to discontinuation) will be summarized by cohort and dose group and for all subjects in the SAF for the entire study period, during each of the 16 hour dose escalation periods and over the post infusion period. Adverse events (number and percent) will be presented by system organ class and MedDRA preferred term.

In addition, a summary of AEs by preferred term and severity, using the worst reported severity grade for each event for the subject, will be provided. The number and percentage of patients with AEs possibly related to study medication will be summarized by age cohort and dose group and for all patients as well. These summaries will be presented for the entire study period, during each of the 16 hour dose escalation periods and over the post infusion period, respectively.

Death (if any) will be summarized by system organ class and MedDRA preferred term as well. AEs, SAEs and death will be also presented in data listings at individual patient level.

Laboratory, vital signs, body weight and decreased blood pressure events

Laboratory data will be summarized by presenting shift tables using extended normal ranges (baseline to most extreme post-baseline value), summary statistics of raw data and change

[REDACTED]

[REDACTED]

from baseline (mean, confidence interval, median, standard deviation, 1st and 3rd quartiles Q1 and Q3) at each assessment time point by age cohort and dose group and for all subjects. Notably abnormal values for individual subjects will be flagged in data listings.

Vital sign data and clinical assessments (including HR, SBP and DBP, ventilation parameters etc. as described in [Section 6.5.2](#) excluding the efficacy variables specified in [Section 6.4.1](#)) will be descriptively summarized as appropriate by presenting absolute values and change from baseline at each assessment time point for each age cohort and dose group and for all patients. In addition, respiratory parameters including FiO₂, and oxygenation index (FiO₂×MAP)/PaO₂ (for patients on mechanical ventilation only), and PaO₂/FiO₂ ratio, will also be summarized by presenting absolute values and change from baseline at each assessment time point by age cohort, dose group and ventilation mode.

The absolute values and change from baseline at each visit in body weight will be summarized descriptively by age cohort and dose group and for all patients.

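### SAP Section 10 gives treatment-emergent adverse events no stated end and omits the protocol's dose-period and post-infusion tables, so events during the 48-hour infusion cannot be told from later ones

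*SAP*

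**What the plan says.** SAP Section 10: "A treatment emergent adverse event is defined as an adverse event that occurs at or after the start of the study treatment". No upper limit follows. Treatment-emergent events (non-serious, serious, all, and those leading to discontinuation) are "summarized descriptively (using number and percentage) by age cohort within each treatment group and in the overall group", then by system organ class and preferred term. Deaths are handled similarly. All adverse events are also listed by patient, and SAP Section 6 lists infusion start and end dates and times.

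Protocol 9.5.2 asks for more. Adverse events, SAEs and events leading to discontinuation are to be summarized "for the entire study period, during each of the 16 hour dose escalation periods and over the post infusion period". It repeats the same three-part split for the severity and relatedness summaries.

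On duration, Protocol 5.1.1 says: "Escalating doses of serelaxin will be administered in a continuous iv infusion for a total of 48 hours". Protocol 5.5.4 and 5.5.5 treat 48 hours as a ceiling. Follow-up is much longer: "Patient participation will be completed 28 days after the start of the study drug infusion" (Protocol 5.5.13), and SAEs "until 30 days after the last study visit must be reported to Novartis" (Protocol 7.2.2), with later ones reported only if a causal link is suspected. Protocol 6.5.1 has physical-examination findings "up to and including Day 14, which meet the definition of an AE must be recorded on the Adverse Event section" of the eCRF. The visible text gives no single closing date for non-serious events.

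SAP Section 1 explains that the study ended early, that the full set of planned analyses might not be meaningful, and that an abbreviated report is planned. Addendum 1, issued after database lock, adds PK concentration and hemodynamic summaries but changes nothing for adverse events.

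**The concern.** Safety and tolerability is one of two primary objectives, and every enrolled child receives serelaxin (Protocol 5.3). Without a comparator, the time of an event relative to the infusion, and to the dose step in force, is one of the few pieces of evidence that can separate a drug effect from the course of the illness.

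The Section 10 tables lose that information in two ways. An event in hour 2 of the infusion and one in week 4 fall in the same row. The two dose groups also overlap (3/10/30 and 10/30/100 µg/kg/day), so a whole-study table by dose group cannot show whether an event arose at 3, 10, 30 or 100 µg/kg/day or after the drug had stopped. The one other dose-resolved safety table in Protocol 9.5.2, confirmed blood pressure decrease events by dose level, becomes a patient listing in SAP Section 11. No tabulated safety summary by dose level remains.

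**Working it through.** **1. The plan's own adverse event figure.** SAP Section 13 gives the chance of seeing, at least once, an event with a 24% occurrence rate:

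- n = 6: 1 − 0.76^6 = 0.807, stated as about 80%.
- n = 3: 1 − 0.76^3 = 0.561, stated as about 56%.

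Both reproduce. Section 13 frames these chances per combination of cohort and dose, but Section 10 has no table by dose level in which such an event could be seen.

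**2. What was planned and what is kept.**

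| Summary of adverse events | Protocol 9.5.2 | SAP Section 10 |
|---|---|---|
| Entire study | yes | yes, from infusion start, no stated end |
| Each 16-hour dose period | yes | no |
| After the infusion | yes | no |

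**3. Share of counted time after the infusion.** Inputs: infusion 2 days (Protocol 5.1.1); examination findings to day 14 (6.5.1); participation to day 28 (5.5.13); SAEs to 28 + 30 = day 58 (7.2.2, taking the day 28 contact as the last visit). Share = (D − 2)/D.

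- D = 14: 12/14 = 85.7%
- D = 28: 26/28 = 92.9%
- D = 58: 56/58 = 96.6%

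**4. Share of events after the infusion.** This needs the event rate over time, which the documents do not give. Two sets of assumptions show how wide the answer is.

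(a) Event rate during infusion = RR times the rate afterwards. Share after = (D − 2)/[(D − 2) + 2·RR].

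| RR (assumed) | 14 days | 28 days | 58 days |
|---|---|---|---|
| 1 | 86% | 93% | 97% |
| 5 | 55% | 72% | 85% |
| 10 | 38% | 57% | 74% |

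The share is exactly one half at RR = (D − 2)/2, that is 6, 13 or 28. Above that, events during infusion are the majority.

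(b) Event rate decaying from infusion start with half-life h days, over 28 days. Share after = (2^(−2/h) − 2^(−28/h))/(1 − 2^(−28/h)). For h = 1, 2, 3 and 7 the results are 25%, 50%, 63% and 81%.

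Across these assumptions the share of events runs from about 25% to 97%. Only the share of time in step 3 rests on the documents.

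**5. Can the split be recovered?** SAP Section 6 lists infusion start and end with clock times. Protocol 7.1 describes adverse events by start and end dates and mentions no clock time. Joining the two listings separates events clearly before or after the infusion end date. It leaves events on that date, and those on days when the dose step changed, without a unique assignment.

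**The case against.** The strongest reply has four parts.

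- **The reduction is declared.** SAP Section 1 cites early termination, and cells of 3 to 6 children were planned even at full enrollment. This explains an abbreviated report. It does not explain why the adverse event, SAE and death tables that were kept should lose their time split, which is no less useful in a small uncontrolled study. Addendum 1 later added hemodynamic summaries before each dose escalation, at 48 hours and at 24 hours after infusion, so time-resolved tables were thought worthwhile for secondary endpoints.
- **The retained table is in the protocol too.** This is correct. Protocol 9.5.2 wants an entire-study summary, so the loss is the companion tables.
- **The window is bounded in practice.** This is also correct. A reader might infer an unlimited count, but the day 28 end of participation and the SAE collection period close it. What is missing is a stated end in the definition.
- **The data stay visible.** Patient listings of adverse events and infusion times, and of blood pressure decrease events where available, allow a partial reconstruction. This lowers the stakes, but the reader must do the join by hand and meets the date-only ambiguity.

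A reader might also infer that the tables mostly count the later course of the illness, or that they inflate the rate attributed to the drug. The documents support neither. Observation is front-loaded: every 2 to 4 hours on infusion, every 4 hours for the next 24 hours, every 8 hours in hospital to day 5, then a day 14 visit and a day 28 telephone contact. Events in acutely ill children may cluster early as well. SAP Section 1 summarizes categorical data by patients, so a child with the same preferred term during and after infusion would count once, and a share of events is not a share of the table. The treatment-emergent label is temporal and makes no causal claim.

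**Conclusion.** The point stands as a gap in presentation. Section 10 gives the treatment-emergent window no stated end and leaves out the dose-period and post-infusion summaries that Protocol 9.5.2 specifies. The retained tables therefore cannot separate events during infusion from later ones, in a study with safety as a primary objective and no control arm.

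The size that can be stated is a share of time: 86%, 93% or 97% of a 14-, 28- or 58-day window falls after the infusion. This assumes a full 48-hour infusion and, for 58 days, a last visit at day 28; a shorter infusion raises the share slightly. No share of events, and no bias in a drug-attributed rate, can be derived from the documents. The patient listings soften the consequence without removing it.

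**What to change.** In SAP Section 10:

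1. Keep the whole-study total and add two columns, infusion and post-infusion, to the adverse event, SAE and death tables. Divide at each patient's recorded infusion end, since some infusions stop before 48 hours.
2. Add the three 16-hour dose periods where onset timing allows. Two columns alone do not restore this part of Protocol 9.5.2. Because Protocol 5.5.4 lets a patient stay on the same dose level for a further period, state whether these columns follow the nominal period or the dose actually given.
3. State how an event with only an onset date is assigned when that date is the infusion end date or a day on which the dose step changed.
4. State the end of the treatment-emergent window, consistent with the collection periods for non-serious events and SAEs.
5. Do not confine the treatment-emergent label to the infusion column; that would take it away from delayed events.

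If the dose-period tables are judged too sparse, say so in Section 10 as a stated departure from Protocol 9.5.2.

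The cost is wording, a small amount of programming and sparser cells. Infusion times and adverse event dates are already recorded. Addendum 1 shows a route for adding descriptive tables after database lock.
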